Control Intervention Group (Enough Snuff Cessation Booklet and Motivational Text Messages)

Figure 4: Enough Snuff Cessation Booklet

Original Enough Snuff

Intervention: The Enough Snuff Intervention is a self-help cessation booklet paired with two brief motivational phone counseling calls that occur one week after the cessation booklet is sent and the week of the set quit date. The first call focuses on increasing motivation for quitting (e.g. reasons for quitting),

setting a quit date, and choosing a quit method. The second call focuses on dealing with tough situations when quitting and following through on quit plans. The Enough Snuff program has been shown to be efficacious in promoting smokeless tobacco cessation with quit rates ranging from 16-18%^{43,44} and is an intervention endorsed by the NCI in their Research-Tested Intervention Programs (RTIPs).⁴⁵ For the

current study we are delivering the program as follows:

Enough Snuff Cessation Booklet: We will provide all control participants with the Enough Snuff Cessation Booklet developed by our consultant [name]. The manual is organized around four key steps to quitting: 1) evaluating readiness and motivation to quit; 2) setting a quit date and selecting a quit plan; 3) dealing with withdrawal symptoms; and 4) maintaining quit status. We will send all participants a link to the manual via text-message as well as mailed a hard-copy of the booklet.

Motivational Text-Messages: To deliver the most equivalent intervention to the original *Enough Snuff* Program, we will send participants motivational text messages that map to the content of the phone counseling sessions. One week after the cessation booklet is sent we will text participants twice a week for the next 5 weeks. We will model the messages after the phone content and messages will focus on: motivation to quit (Week 1), setting a quit date (Week 2), picking a quit plan (Week 3), motivation to follow-through with plan (Week 4) and dealing with tough situations when quitting (Week 5). Messages will refer to the Enough Snuff booklet ask for a response from participants (See **Table 8**). We chose to send text messages to participants instead of phone calls as texting is consistent with our mode of contact with participants, less expensive, expands our reach, and is highly acceptable according to our pilot work.

Intervention Delivery. *Mosio* will manage the technical aspects of the SGR computer-based program, the support messages and the motivational messages in the control group. *Mosio* will provide the two-way text messaging platform that we will use for this study. This platform allows to communicate with participants, collect data and contact participants via mobile text-messaging for follow-up. This is the same company and program our team successfully used as the texting platform for our pilot and was approved by our Information Security Office. The **Participant interface** with the intervention will be entirely through SMS messaging. Outbound messages from the intervention to participant will pass through an SMS gateway that queues each message, delivers it to the cell provider (which passes to the participant's phone), and returns delivery status (success or failure) to the intervention application. Inbound messages from participants to the intervention, such as a reply indicating whether they chewed, will be queued at the gateway and retrieved each minute by the application. **Study staff interface** with the intervention through a web-based dashboard and email messages from the application. Through the dashboard, staff will see aggregate information and can identify individual participants by criteria such as SGR status and drill down to their detailed data. Manual outbound SMS messages can be delivered from the dashboard using templates or freeform (for example, to respond to a participant who has requested help via SMS).

Table 8. Example Text Messages Mapped from Enough Snuff Support Phone Calls

Content	Example	Number of Characters
Motivation	Make a list of your reasons for quitting. Text us one reason why you are quitting.	67
Quit Date	Setting a quit date increases your chances of quitting. Pick a date in the next two weeks and give quitting a try. What will be your quit date?	116
Quit Plan	Having a quit plan is important. Think about your plan. Text Y if you have a quit plan.	70
Following Quit Plan	Don't forget your quit plan! Text Y if you have a quit plan. Is your quit plan working to help you reach your goals?	93
Dealing with Tough Situations	Don't tempt yourself- take everything out of your home, car and workplace that reminds you of chewing. What will you remove?	104

Measures

Outcomes and Mediators

Self-report smokeless tobacco cessation will be assessed at the end of treatment, 3 and 6-months post-intervention. **Self-report smokeless tobacco cessation at month 6 will be the primary outcome.**

Secondary outcomes, which will be subsequently evaluated as mediators of the intervention effects, will be assessed at baseline, end of treatment, and 3 and 6-months post-intervention.

Primary Outcome: Smokeless Tobacco Cessation Outcome. Self-reported abstinence from tobacco use will be collected at end of treatment, 3 and 6-months post-intervention. We will measure 7-day point prevalence abstinence by asking participants, "In the past 7 days, have you used smokeless tobacco (chew or dip)?" This binary outcome will be dichotomized as 0=no and 1=yes. We will also randomly select a 20% (10% in control and 10% in intervention arm) of those who report quitting at the end of treatment, 3 and 6 months to biochemically confirm cessation using saliva cotinine strips. NicAlert Semiquantitative test strips will be used and a 10 ng/ml cutoff will indicate exposure. Biochemically validated cessation at each of these assessment points will be coded as 0=no and 1=yes.

Mediator: Craving. We will assess craving using the Smokeless Tobacco Evaluation Questionnaire (STEQ) based on the Cigarette Evaluation Questionnaire (mCEQ) modified for ST users.⁴⁶ The STEQ is a 12-item scale assessing the degree to which participants experience the reinforcing effects of smokeless tobacco on a 7-point Likert scale. The scale has five domains: chewing satisfaction, psychological reward, enjoyment of sensations in cheek/gum, craving reduction, and aversion.

Mediator: Withdrawal. We will assess withdrawal using the self-report seven item Minnesota Nicotine Withdrawal Scale⁴⁷ as has been used in other smokeless tobacco cessation trials assessing withdrawal. This seven-item scale measures withdrawal symptoms (i.e., irritability, anxiety, difficulty concentrating, restlessness, increased appetite or weight gain, depression, and insomnia) and measured on an ordinal scale (0= not present) to 4 (severe). A total score ranging from 0 to 28 will be derived to measure severity of withdrawal symptoms, with higher total scores representing greater withdrawal. Internal consistency of the scales are reported to be between $\alpha= 0.76-0.91$.

Mediator: Self-regulation. We will assess self-regulation using the Short-form Self-Regulation Questionnaire, which is a 31 item self-report survey measuring the ability to regulate behavior and achieve goals.⁴⁸ Participants indicate the extent to which they agree with each item using a 5-point Likert scale: 1 (Strongly Disagree), 2 (Somewhat Disagree), 3 (Neutral), 4 (Somewhat Agree), and 5 (Strongly Agree). The measure has a total scale computed by summing the items, with higher total scores indicating increased self-regulation. Internal consistency of the scale is reported to be $\alpha=0.92$.

Mediator: Restraint. We will measure restraint using a modified version of the Smoking Restraint Questionnaire⁴⁹ for smokeless tobacco by replacing all smoking references with smokeless tobacco. The Smoking Restraint Questionnaire is a four-item survey. The two binary questions of the questionnaire are scored 1 (No) and 5 (Yes). The two multiple-choice items are scored from 1 to 5. Total smokeless tobacco restraint is calculated as the sum of the four items. The minimum possible score is 4 and the maximum possible score is 20, with higher total scores indicating higher levels of restraint. Internal consistency of the scale is reported to be $\alpha=0.74$.

Sample Characteristics : Baseline sociodemographic and clinical measures will be collected to describe the characteristics of the total sample and intervention arms. Many of these measures are potential important moderators or mediators of intervention effects that will be explored after the specific aims are fully examined.

- **Demographics and Relevant Biological Variables.** We will assess age, sex, race, education, marital status, and socio-economic status (SES) at baseline using measures adapted from our prior research.
- **Smokeless and other Tobacco Use History.** At baseline, participants will be asked about their tobacco use habit including: number of chews/dips per day, number of quit attempts in the past year, age of chewing/dipping initiation and past use of other tobacco products including electronic cigarettes.
- **Nicotine Replacement Therapy (NRT) Use:** We will ask participants at all follow-up time points if they have used any NRT including the patch, gum or lozenge.
- **Nicotine Addiction.** We will assess nicotine addiction at all time-points using the Severson Smokeless Tobacco Dependence Scale-Short Form (SSTDS). The SSTDS is a validated questionnaire has eight items with a range of scores from 0-19 with higher scores being most addicted to nicotine.⁴⁷
- **Self-efficacy.** At all time-points we will measure self-efficacy using a similar 9 item scale to the Temptations scale. We will adapt the scale by switching out smoking with chewing/dipping. Sample items read, "How

confident are you that you would not chew in the following situations: when you are very angry about something or someone, when you feel you need a lift, etc." (1=Not at all confident and 5=Extremely confident).

- Alcohol Use Disorder Identification Test (AUDIT-3). At all time-points we will use the AUDIT, a 3 item self-report scale that measures risky drinking, as this may influence quit rates.⁵⁰

Process Measures: Process measures that could impact outcomes will be collected at baseline, during intervention administration, at the end of treatment, 3 and 6 month follow-up.

- Adherence (Intervention Group). Adherence to the SGR intervention will be calculated two ways. First, we will measure time to response from the SGR message. Second, we will create a categorical variable (0=respond in more than 30 minutes, 1=respond after 30 minutes. If a participant responds to less than half of chewing/dipping prompts in one day, we will exclude this day from the adherence analysis examining whether overall adherence predicts quit rate and/or smokeless reduction in the SGR group.
- Adherence (Control Group). Participants will be asked at all follow-up time points how often they read the cessation booklet using a using a 5-point Likert scale (1 = none, 2 = some, 3 = most, 4 = the entire guide, and 5 = the entire guide more than once).⁴⁴
- Satisfaction with Intervention. Participants in both arms will be asked at end of treatment survey 1) "How useful was the intervention in helping you to quit smokeless tobacco?" (Not at all useful=1, Extremely useful =5) and 2) "Would you recommend the program to a friend?" (Definitely would not recommend=1, Definitely would recommend=5).

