We will recruit smokeless tobacco users ($N=500$) and randomize them to receive the SGR intervention ($N=250$) or the Enough Snuff intervention ($N=250$). We will conduct phone-based or smart phone-based assessments with participants at baseline prior to randomization, end of treatment, 3 and 6-month follow-up after intervention completion. The primary outcome will be self-reported 7-day point smokeless tobacco use at 6-months (yes/no). We will biochemically confirm a subset of participants who report quitting via saliva samples using NicAlert test Strips (20% of sample who report quitting split between intervention and control group). NicAlert strips can be used with all tobacco types and have been used with smokeless tobacco users.³⁵ We will randomly select these participants at end of program, 3 and 6-month survey time points as to not confound intervention results. We will conduct a supplemental analysis to compare self-report and biochemically confirmed quit results. The secondary aims are to assess: 1) the efficacy of the text-based SGR intervention compared to the control intervention on changes in withdrawal, craving, self-regulation and restraint across the 6-month period and 2) explore whether changes in withdrawal, craving, self-regulation and restraint mediate intervention effects on self-reported cessation at 6 months post-intervention (Figure 2). We will follow participants regardless of whether they complete or adhere to the intervention.

Design Considerations. We chose our control comparator using guidance from the *Pragmatic Model for Comparative selection in Health Related Behavioral Trials*.³⁶ The main goal of our trial is to compare our new SGR intervention to a well established evidenced-based alternative like the Enough Snuff Intervention. We decided against adding nicotine replacement therapy or varenicline for smokeless tobacco users. A recent

Table 2. Lessons Learned from Pilot and Changes made to Proposal	
Areas for Improvement	Changes for Current Proposal
Length of time for accrual of our sample	Clinic recruitment was not feasible in our pilot. Once we switched to a social media recruitment approach, at the suggestion of [name] our metrics improved significantly. We plan to recruit solely using media outlets (including social media) and will expand our targeted recruitment area to increase reach. [name] will consult on recruitment in the current study.

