4-week reduction period was too short for many smokeless tobacco users	We will extend our reduction period to 6 weeks.
30% attrition rate	High attrition rates (as high as 60%) have been reported in other low touch smokeless tobacco use cessation trials; therefore, we plan to institute text-based check-ins with our participants every 3-4 weeks after the intervention period to increase engagement.
No support after reduction or quit day in SGR group	We will start support messages 2 weeks before the quit date and extend them to 4 weeks after the quit date.

Figure 2: Consort Diagram

Cochrane review found that the quality of evidence for NRT among smokeless tobacco users is low.³⁷ Varenicline has shown efficacy in the short term for smokeless tobacco cessation, however this is based on a recent meta-analysis that contained only three published trials.³⁸ Further, varenicline has increased exclusion criteria, side effects and low adherence levels in smokeless tobacco users.³⁶ Our goal is to have a trial that has the broadest inclusion criteria to reach the largest number of underserved smokeless tobacco users possible.

We also decided against biochemical verification of cessation in this study given that we found it was not feasible in our pilot. Other smokeless tobacco cessation studies also use self-report cessation as the primary outcome.^{37,39} Much like these studies, our study is community-based and has comparable demand characteristics as both arms are interactive. Thus, according to the SRNT Subcommittee on Biochemical Verification (2000) guidelines,⁴⁰ biochemical verification is not feasible or warranted as there is no reason to believe that one treatment will group will lie or give false information relative to another treatment group in this study. However, to further assess feasibility for future work we will biochemically confirm via saliva samples using NicAlert test strips. Twenty percent of the sample who report quitting (split between intervention and control group) of participants will be randomly selected at end of treatment, 3 and 6-month survey time points as to not confound intervention results. We will conduct an analysis to compare self-report and biochemically confirmed quit results overall and by each treatment group.

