We plan to recruit all participants for the current study using social media and other media advertisement outlets (i.e., Facebook, Instagram, Google Ads). As we did in our pilot, we will create an advertising profile for the study targeted to our study population (e.g., smokeless tobacco users (chewer/dipper), over age 18, profiled for tobacco use) for rural and medically underserved counties in the U.S. The advertisement briefly describes the study and links to a project-specific landing page that includes project branding (e.g., study logo, name, and Duke University association), a simple contact form with name, phone number, email and two simple baseline questions (e.g., “Do you use smokeless tobacco (chew/dip) every day and use at least one or more tins/cans per week or more?” and “Please provide your zip code”). After they enter their information, a member of the study team can call to collect more information to determine if they meet the criteria for participation in the study. Targeting rural and medically underserved counties in North Carolina and four rural counties in South Carolina for our pilot study, we were able to recruit 70 smokeless tobacco users in one year

Table 4. Rural Counties

State	% Rural Counties
Wyoming	91
Montana	69
Mississippi	79
Oklahoma	76
Kentucky	70
West Virginia	60

(approximately 5-6 per month) using these methods. Data from our targeted marketing profiles show Facebook and Instagram ads reached 15,147 people total over 30 days resulting in 22,055 ad views and 121 link clicks per month with a monthly advertisement budget of \$200. To increase our recruitment numbers for the current study we plan to: 1) target rural and medically underserved counties nationally with high smokeless tobacco use rates; 2) increase our Facebook budget and work with [name] recruitment consulting firm to manage our media platforms and 3) change ad messaging, demographic targeting and geographic targeting weekly to ensure we are recruiting a diverse sample. Even if we estimate similar, very conservative recruitment metrics as seen in our pilot, given our increased reach with national recruitment we anticipate we can recruit at least 168 participants a year (or 14 per month) from our proposed (social) media recruitment methods. Given our 3-year recruitment time frame, we anticipate having ample time to achieve the target enrollment of participants for this study.

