Follow-up assessments will be conducted over the phone or a smartphone option will be available for survey completion at the end of treatment, 3 and 6-months post-intervention. Study data collectors will be blinded to study arm. Our two research assistants will document who randomized each participant and will not conduct the follow-up assessment with those participants. We will obtain follow-up data on all participants regardless of adherence or completion of treatment. The follow-up rate in our pilot study was >70%, and we will use similar strategies to obtain follow-up data. To increase this follow-up rate, we also will maintain regular contact with participants in-between the end of program 3 and 6-month follow-up using cards, e-mails, and study updates summarizing study results. We will also use a graded compensation for surveys with \$10 for baseline \$15 for end of program, \$20 for 3 months and \$25 for 6-month follow-up. Participants will receive a bonus of \$25 for completing all assessments.

Randomization. The target sample will be eligible and enrolled participants randomized to either the SGR (N=250) or control (N=250) intervention group. Computerized randomization will be used to deliver a permuted block randomization with block sizes of four that will be used to randomly assign participants to one of the two intervention groups. The randomization scheme generated by the study statistician will be administered using the REDCap system.

Interventions:

SGR Intervention Group. We will send those in the SGR intervention group a 6-week text-based scheduled gradual reduction intervention and 6 weeks of support text-messages. Typical SGR interventions have lasted for 4 weeks. We have increased our program to 6 weeks based on feedback from our pilot.

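### Retention updates may carry undefined study results to participants whose self-reported primary outcome is still pending

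*Protocol*

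**What the plan says.** The Protocol, Recruitment and Data Collection, gives the purpose and the recipients: "To increase this follow-up rate, we also will maintain regular contact with participants". The same sentence places this contact between end of program and the 3- and 6-month follow-ups, and names the means: "cards, e-mails, and study updates summarizing study results". The Protocol does not say what study results means here, whether results would be pooled or by arm, or when they may first be sent.

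These other statements bear on the point:

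- **Outcome.** Overall Strategy and Measures make the primary outcome a single self-reported yes/no answer about the past 7 days, taken at month 6.
- **Blinding.** "Study data collectors will be blinded to study arm". No blinding of participants is described. The two programs look different to those who receive them: scheduled texts with a reduction plan in one arm, a booklet with motivational texts in the other.
- **Accrual.** "Given our 3-year recruitment time frame" (Study Setting and Sample), at an anticipated 14 participants a month.
- **Reliance on self-report.** Design Considerations defends it on the ground that "there is no reason to believe that one treatment will group will lie or give false information relative to another treatment group".
- **Missing outcomes.** The SAP, Handling of Missing Data, counts them as not having quit in the primary analysis.
- **Interim looks.** The SAP describes none.

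**The concern.** The sentence states an action, so this is more than a missing detail. Staff who follow it as written could tell participants how the study is turning out before those participants answer the primary outcome question. Participants can tell which program they are receiving. News that one program is doing better or worse could change what they report, or whether they respond at all. Either change enters the primary comparison directly: the first through the self-reported answer, the second through the rule that a missing answer means not quit.

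The Protocol accepts self-report because neither arm is thought to have more reason than the other to misreport. Sharing results by arm could supply such a reason, so the retention plan could undercut the Protocol's own case for its endpoint.

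**Working it through.** **1. Could results exist while outcomes are pending?** The inputs are 14 enrolled per month and 500 in total (Protocol, Study Setting and Sample; Overall Strategy). The active period is 6 weeks if it ends at quit day, or 10 weeks if it includes the four weeks of support messages afterwards (Protocol, Interventions).

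- 6 weeks is 1.4 months, so the first month-6 outcome arrives 1.4 + 6 = 7.4 months after first enrolment. About 14 × 7.4 ≈ 103 people are enrolled by then and about 397 are not.
- 10 weeks is 2.3 months, which gives 8.3 months, about 116 enrolled and about 384 not.

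End-of-treatment results would exist about six months sooner. Early results would therefore be available for most of the trial.

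**2. Does anything in the documents stop their release?** The retention sentence allows study results in the updates. The blinding statement covers data collectors only. The SAP has no interim analysis that would produce or govern results. Nothing limits the updates to accrual news, to pooled figures, or to the time after the last month-6 assessment.

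**3. The plan's own power figure.** With n = 250 per arm, power = Φ[(|p1 − p0| − 1.96·s0)/s1], where s0 = √(2·p̄(1 − p̄)/n) and s1 = √([p1(1 − p1) + p0(1 − p0)]/n). For 25% against 12%, p̄ = 0.185, s0 = 0.0347 and s1 = 0.0342, so (0.13 − 0.0681)/0.0342 = 1.81 and power is 96.5%. The SAP states 96%, so the figure reproduces. The point does not depend on it, but it gives a base for sensitivity.

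**4. Sensitivity to false reports of quitting.** Let a fraction f of non-quitters falsely report quitting, so that the reported rate is p + (1 − p)·f. Every value of f is an assumption; the documents give none.

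| Case | True rates, SGR / control | f | Reported rates, SGR / control | Result |
|---|---|---|---|---|
| Equal in both arms | 12% / 12% | any | equal | type I error unchanged |
| Equal in both arms | 25% / 12% | 5% | 28.75% / 16.4% | power 91% |
| Equal in both arms | 25% / 12% | 10% | 32.5% / 20.8% | power 84% |
| SGR arm only | 12% / 12% | 2% | 13.76% / 12% | chance of a significant result favouring SGR 8% (nominal 2.5%) |
| SGR arm only | 12% / 12% | 5% | 16.4% / 12% | the same chance, 29% |
| Control arm only | 25% / 12% | 2% | 25% / 13.76% | power 89% |
| Control arm only | 25% / 12% | 5% | 25% / 16.4% | power 66% |

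The equal case costs some power. Only a differential effect distorts the comparison.

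**5. Retention.** Because missing counts as not quit, the analysed rate is retention × quit rate among responders. At the pilot's 70% retention, an analysed rate of 12% means 0.12/0.70 = 17.1% among responders. If updates raised retention in one arm only, and the extra responders quit at that same rate, each added percentage point of retention would add about 0.17 points to that arm's rate with no false reporting at all.

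**The case against.** The strongest reply is that the phrase is loose wording in a list of retention tools. Study results may mean accrual news, baseline summaries or pooled figures, and the text never mentions quit rates or results by arm. The SAP plans no interim look, so no planned step produces a comparison by arm during follow-up. The contacts are described for participants in general, which suggests the same updates for both arms, and an effect common to both arms does not inflate type I error. If an update makes people truly quit, it acts as a co-intervention and not as misreporting. There is also some checking of the outcome: "Twenty percent of the sample who report quitting" are to be tested by saliva strip, with agreement compared between arms.

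Most of this stands, and it limits how far the point goes. It does not remove the point. The text says results, and nothing confines it to the harmless meaning. The lack of a planned interim look does not rule out informal or pooled tallies. The saliva check is supplemental and does not protect the primary analysis.

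Two stronger readings are tempting. A reader might infer a type I error of about 15%. The arithmetic is right for 18% against 15% with 250 per arm (14.7%), but it assumes a 3-point rise in one arm only, and neither that rise nor the 15% base rate comes from the documents. A reader might also infer that staff who prepare the updates see accumulating results. The documents do not say who prepares them or what they see, and nothing shows that the data collectors' blinding is broken.

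**Conclusion.** The concern holds in conditional form. As written, the Protocol permits outcome results to reach participants before their self-reported primary outcome is collected, and neither document restricts or delays this. Harm to the comparison requires that results be shared by arm or affect the arms differently, through reporting or through retention. The documents do not say that either would happen.

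The size of any bias cannot be estimated from the documents, and the one-arm cases in the table are purely assumed. They show only that, at 250 per arm, small arm-specific shifts would matter. The change is worth making because the text states an action, the endpoint rests on self-report, and correction costs almost nothing.

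**What to change.** In the Protocol, Recruitment and Data Collection:

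- Delete the last three words of the list of retention tools, so that it ends at study updates.
- Limit the updates to non-outcome content, such as recruitment milestones and appointment reminders, identical in both arms.
- Add a sentence that no outcome results, overall or by arm, will go to participants or data collectors until the last month-6 assessment is complete.

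The cost is a brief text change. The number and timing of retention contacts, the sample size and the analysis are unaffected.

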Inclusion criteria will include: 1) 18 years of age and older, 2) Have used smokeless tobacco for the last year, currently (past 30 days) uses smokeless tobacco daily, and use of at least one or more tins/cans per week 3) Have an address in a rural census tract defined by a RUCC code of 4-10 and/or an IMU of 62 or lower; 4) Interested in participating in a cessation program; and 5) Have access to a cell phone with unlimited texting ability. **Exclusion criteria** include: 1) Non-English speaking; 2) Have smoked cigarettes or used any other tobacco product in the past 30 days (i.e., dual user); and 3) Currently participating in a smokeless tobacco cessation study. We are excluding dual users (those who use both cigarettes and smokeless tobacco) who plan to continue to smoke cigarettes. It is too challenging to promote scheduled gradual reduction when participants use more than smokeless tobacco. We will track how many participants are not eligible for this study because they do not meet this eligibility requirement. We did not exclude anyone from our pilot for not having his or her own cell phone or for using multiple tobacco products.

Recruitment and Data Collection. Advertisements for the study will be placed on Facebook, Instagram and Google Ads. For example, Facebook users will be shown an advertisement that shows a quit smokeless tobacco related image and quit smokeless tobacco related messaging (**Figure 3**). Users who click on that advertisement will then be taken to a project-specific landing page that includes project branding (e.g., study logo, name, and Duke University association), a simple contact form with name, phone number, email and simple baseline question (e.g., “Do you use smokeless tobacco (chew/dip) every day and use at least one or more tins/cans per week or more?” and “Please provide your zip code”). Research staff will call these participants to screen them for eligibility and set up a baseline/enrollment phone visit where informed consent will be obtained and baseline study measures collected. All participants will be asked to provide the three best contact methods and times to reach them and contact information of two people the study staff could contact should they have issues reaching the participant.

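### One fixed block size of four, not stated to be withheld from staff, could make 8% to 33% of assignments certain in advance and weakens the assessor blinding

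*Protocol*

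**What the plan says.** Protocol, Randomization: participants are "randomized to either the SGR (N=250) or control (N=250) intervention group" by "permuted block randomization with block sizes of four". On generation and delivery: "The randomization scheme generated by the study statistician will be administered using the REDCap system". No second block size, random variation of size or stratification factor appears in either document. Neither says that the size is withheld from those who enrol or assess.

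Protocol, Recruitment and Data Collection, on screening: "Research staff will call these participants to screen them for eligibility and set up a baseline/enrollment phone visit". On follow-up: "Study data collectors will be blinded to study arm". The mechanism given is a cross-over rule: "Our two research assistants will document who randomized each participant and will not conduct the follow-up assessment with those participants".

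Protocol, Intervention Delivery: through the texting dashboard, staff "can identify individual participants by criteria such as SGR status".

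Protocol, Measures: the primary outcome is self-reported 7-day abstinence at month 6. Follow-up is by telephone or smartphone survey. Only 20% of those who report quitting are selected for saliva testing.

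**The concern.** In a 1:1 block of four the last assignment is always fixed by the first three, and the third is fixed whenever the first two agree. Anyone who knows the block size and follows the sequence can work this out, whatever the software conceals. The Study Setting and Sample section plans for about 14 participants a month, or 14/4 = 3.5 blocks, which is slow enough to follow.

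Two things are at stake. The first is allocation concealment: staff who expect a particular arm could change the timing of an enrolment or how strongly they encourage it. One inclusion criterion, interest in a cessation programme, leaves room for judgement. The primary Aim 1 analysis is a logistic regression without covariates, and motivation to quit is not among the listed baseline measures, so selection on it could not be adjusted for. The second is assessor blinding. The cross-over rule keeps an assistant away from participants they randomised themselves. It does not stop that assistant from deducing the arms of the other's participants from the gaps in the sequence.

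**Working it through.** **The plan's own figure.** The documents give no figure for predictability. The related stated figure is 96% power (SAP, Statistical Power: 250 per arm, 25% against 12%, two-sided 0.05). With a mean rate of 0.185:

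z = [0.13 × √250 − 1.96 × √(2 × 0.185 × 0.815)] / √(0.25 × 0.75 + 0.12 × 0.88) = (2.055 − 1.076) / 0.541 = 1.81, so power = 96.5%. The stated figure reproduces.

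**Case A: all earlier assignments are seen.** A block of four has 6 equally likely sequences.
- Certain in advance: position 4 always and position 3 in 1/3 of blocks. (0 + 0 + 1/3 + 1)/4 = 1/3 = 33.3%, about 167 of 500.
- Best guess correct: (1/2 + 2/3 + 2/3 + 1)/4 = 70.8%, where 50% means no information.

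**Case B: an assistant knows only their own assignments and the list order.** Let f be the chance that any earlier assignment was their own. The documents give no f; 1/2 is assumed, independently for each slot.
- Next assignment certain: position 3 needs both earlier ones known and equal (f²/3); position 4 needs both opposite-arm members known (f²). (f²/3 + f²)/4 = f²/3. At f = 1/2 this is 8.3%, about 42 of 500. At f = 1 it returns Case A.
- Best guess correct at f = 1/2: the four positions give 0.500, 0.583, 0.625 and 0.688, with mean 59.9%.
- Looking back at a participant randomised by the other assistant: the arm is certain when both opposite-arm members of the block are the assistant's own, so f² = 25%. The best guess is right 68.8% of the time.

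The retrospective figure depends on f. As illustrations, f = 0.3 gives 9% and f = 0.7 gives 49%.

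**Effect of varying the size.** Lists of 500 were simulated (400 repeats) against a guesser who sees all past assignments and knows the set of sizes, but not the size of each block.

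| Scheme | Certain | Predicted with probability ≥ 80% | Best guess correct |
|---|---|---|---|
| Fixed 4 | 33.3% | 33.3% | 70.8% |
| Random 4, 6, 8 | 2.2% (about 11 of 500) | 25.1% | 68.0% |
| Random 2, 4, 6 | 4.3% (about 21 of 500) | 52.4% | 70.2% |

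Including blocks of two brings little gain in guessing accuracy and raises the share predicted with high probability.

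**Cost in balance and power.** The largest running imbalance is half the largest block: 4/2 = 2 now, 8/2 = 4 with sizes 4, 6 and 8. The final difference between arms in the simulations was at most 4. At 248 against 252, power is 96.5%, unchanged.

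**The case against.** Fixed permuted blocks run through an electronic system are a recognised design, and nothing here contradicts the plan or its power. The 33% figure needs staff to see the whole sequence. The documents do not establish that, and they describe data collectors as blinded. This stands, and it is why the range from 8% to 33% is given.

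The route to selection is also narrow. Baseline assessment precedes randomisation, most eligibility items are factual, and with two people randomising, the next slot is hard to target from a booking made earlier. This stands in part: it limits deliberate steering but does not affect the retrospective inference that weakens blinding.

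The dashboard may be a more direct route to unblinding than any arithmetic on blocks. If assessors can use it to pick out SGR participants, changing block sizes does not restore their blinding. That stands as a separate problem. The smartphone survey may also bypass the telephone assessor for some participants.

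A reader might infer several stronger things. One is that the two assistants screen, enrol and randomise everyone. The Protocol ties them to randomising and, by implication, to follow-up; screening is given only to research staff. Another is that the block size was public during enrolment. Nothing shows this, although study staff would ordinarily hold the protocol. A third is that varying the sizes removes the problem at no cost. The table shows that the best guess stays right about 68% of the time, and a switch during the trial carries some administrative work.

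**Conclusion.** The point holds as a modest design weakness with a cheap improvement available. The fixed size is stated and the enumeration is exact. Which figure applies depends on what staff can see, which the documents leave open: 33% certain and 71% guessed correctly with full sight, 8% and 60% with sight of one's own assignments only. In the second case, 25% of the participants an assistant would assess can be identified by arm.

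The conclusion rests on four assumptions: a single unstratified list (inferred from silence), staff knowledge of the block size, knowledge of the list order and, for the partial case, an even and random split between the assistants. The 25% figure also takes the cross-over rule to mean that each assistant assesses the other's participants. Nothing suggests that anyone has exploited the predictability, and the sample size and power are unaffected.

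**What to change.** For any list not yet used, the study statistician should generate randomly varying block sizes, for example 4, 6 and 8. The sizes should sit in a restricted document that enrolling and assessing staff cannot see; the protocol would say only that sizes vary and are withheld. The Protocol should also state who screens, who randomises, who assesses and whose assignments each can see.

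The cost is a regenerated REDCap list, one restricted document and, if the switch comes during enrolment, a documented change to the randomisation procedure. The running imbalance may reach 4 participants instead of 2, with no loss of power. If enrolment is complete, the report should give the block size and say who could see assignments, as a limitation.

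This change does not close the dashboard route. Whether assessors can see SGR status there needs to be settled separately.
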